7.5.1.1 Adverse events

The coding dictionary for this study will be MedDRA 11.1. It will be used to summarize AEs by SOC and PT. Subjects reporting more than one AE for a given MedDRA PT will be counted only once for that term. Subjects reporting more than one AE within a SOC will be counted only once for the SOC total. Subjects reporting more than one AE will be counted only once in the overall AE total.

SOCs will be presented by descending frequency for "Total" (RAJ1 + RAJ3 + RAJ4) column, and PTs within SOC will be presented by decreasing frequency in "Total".

Number and percentage of subjects with TEAE in the following AE categories will be summarized by SOC and PT:

An overview table will include the following details:

- Number and percentage of subjects with TEAE
- Number and percentage of subjects with drug related TEAE
- Number and percentage of subjects with death
- Number and percentage of subjects with serious TEAE
- Number and percentage of subjects with drug related serious TEAE
- Number and percentage of subjects with Grade 3 or Higher in Severity TEAE
- Number and percentage of subjects with TEAE leading to permanent discontinuation of study drug
- Number and percentage of subjects with drug related TEAE leading to permanent discontinuation of study drug
- Number and percentage of subjects with serious TEAE leading to permanent discontinuation of study drug
- Number and percentage of subjects with drug related serious TEAE leading to permanent discontinuation of study drug
- Number and percentage of subjects with TEAE leading to dose decrease of study drug
- Number and percentage of subjects with drug related TEAE leading to dose decrease of study drug
- Number and percentage of subjects with TEAE leading to temporary discontinuation of study drug
- Number and percentage of subjects with drug related TEAE leading to temporary discontinuation of study drug

The number and percentage of subjects with TEAEs, as classified by SOC and PT will be summarized by preceding studies and overall. Summaries will be provided for:

- TEAEs
- Drug related TEAEs, defined as any TEAE with possible, probable or missing relationship to study drug as assessed by the investigator.
 Subjects reporting more than one TEAE for a given PT will be counted only once for that term in the most related category reported.

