In addition, the number and percentage of subjects with TEAEs and Drug related TEAEs, as classified by SOC and PT will be presented by preceding studies and overall, by Maximum Dose of Study Drug.

- Serious TEAEs
- Drug related serious TEAEs
- TEAEs by severity based on National Cancer Institute Common Terminology Criteria for Adverse Events (NCI-CTCAE) Grade (Grade 1 = mild, Grade 2 = moderate, Grade 3 = severe or medically significant, Grade 4 = life threatening, Grade 5 = death related to AE)

Subjects reporting more than one TEAE for a given PT will be counted only once for that term in the most severe category reported.

If a subject has an AE which has a missing severity, then the subject will be counted in the severity category of "Missing" (i.e., missing severity will not be imputed).

- Drug related TEAEs by severity
- Grade 3 or higher TEAEs by severity
- TEAEs by relationship to study drug

Subjects reporting more than one TEAE for a given PT will be counted only once for that term in the most related category reported.

TEAE with missing relationship to study drug missing will be counted as drug related. Moreover, any TEAE with missing relationship to study drug or reference drug was counted as drug related (probable).

- TEAEs leading to death
- TEAEs leading to permanent discontinuation of study drug
- Drug related TEAEs leading to permanent discontinuation of study drug
- Serious TEAEs leading to permanent discontinuation of study drug
- Drug related serious TEAEs leading to permanent discontinuation of study drug
- TEAE leading to dose decrease of study drug
- Drug related TEAE leading to dose decrease of study drug
- TEAE leading to temporary discontinuation of study drug
- Drug related TEAE leading to temporary discontinuation of study drug
- Most common TEAEs (> 5% in any preceding study)
- Most common serious TEAEs (> 5% in any preceding study)
- TEAEs excluding serious adverse events that equal to or exceed a threshold of 5% in any preceding study
- The number and percentage of subjects with TEAEs of special interest.

Following adverse events of special interest are defined:

- Serious Infections
- Malignancies
- Herpes Zoster Related Disease (Herpes Zoster and Varicella)
- Herpes Zoster
- o Varicella

Infections That Require Intravenous Anti-infectious Therapy

Note: Definition will be provided in 10.8 Appendix 8: AE of Special Interest.

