7.5.1.2 Adverse Events Per 100 Patient-Years

In order to adjust for differences in subjects' durations in the study and the potential differential dropout rates between the preceding studies, TEAEs per 100 patient-years (PYs) will be calculated as follows:

Definition 1:

TEAEs per $100 \text{ PYs} = 100 \times \text{(Number of subjects who had at least 1 incidence / Total PYs)}$ Total PYs will be calculated by summing individual subjects' durations.

If subjects had at least 1 predefined AE, then the duration of these subjects are summed as from initial dose up to first incidence of predefined AEs.

If subjects had no predefined AE, then the duration of these subjects are summed as from initial dose through follow-up. Summed duration will be divided by 365.25 to represent per year.

Definition 2:

TEAEs per 100 PYs = $100 \times (Number of TEAEs for all subjects/ Total PYs)$

For number of TEAEs for all subjects, multiple occurrences of the same TEAE in the same subject will be counted multiple times.

Total PYs will be calculated by summing subjects' durations in this study through the follow-up period. Each subject's duration will be calculated as: (last date of follow-up in the study – date of initial dose of study drug + 1) / 365.25.

The number of TEAEs and TEAEs per 100 PYs will be provided by Definition 2, for all TEAEs (if analyzable) by SOC and PT for each preceding study, and Total.

Patient-Year analysis for following specified AE will also be conducted by Definition 1 with 95% confidence interval.

- Serious Infections
- Malignancies
- Herpes Zoster Related Disease (Herpes Zoster and Varicella)
- Herpes Zoster
- o Varicella
- Infections That Require Intravenous Anti-infectious Therapy

Note: Definition will be provided in 10.8 Appendix 8: AE of Special Interest.

Confidence Interval for TEAEs per 100 patient-years will be calculated for AE of special Interest based on following formula (assuming Poisson distribution).

- Upper limit of CI (TEAEs per 100 PYs): $100 \times \exp(\log(A/T) + Z_{(alpha)} * \sqrt{1/A})$
- Lower limit of CI (TEAEs per 100 PYs) : $100 \times \exp(\log(A/T) Z_{(alpha)} * \sqrt{1/A})$

A: Number of subjects who had at least 1 incidence

T: Total PYs

Z_(alpha): alpha % point of standard normal distribution

alpha = 0.025

TEAE of special interest per 100 patient-years analysis will be displayed the following category.

- \circ 0 6 months
- \circ 6 <- 12 months
- o 12 <- 24 months
- o 24 <- 36 months

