10.8 Appendix 8: AE of Special Interest

1. Serious Infections

AE which belongs to SOC of Infections and infestations (10021881) and regarded as serious.

2. Malignancies

Following PT terms are included.

Diffuse large B-cell lymphoma (10012818), Bladder cancer (10005003), Breast cancer (10006187), Carcinoma in situ (10061450), Colon cancer (10009944), Gastric cancer (10017758), Renal cancer (10038389), Squamous cell carcinoma (10041823), Small cell lung cancer stage unspecified (10041071), Extraskeletal chondrosarcoma (10015838), Lymphoma (10025310), Thyroid cancer (10066474).

3. Herpes Zoster Related Disease (Herpes Zoster and Varicella)

Following PT terms are included.

Herpes zoster (10019974), Herpes zoster iridocyclitis (10019980), Herpes zoster ophthalmic (10019983), Herpes zoster multi-dermatomal (10058428), Herpes zoster infection neurological (10061208), Herpes zoster oticus (10063491), Herpes zoster disseminated (10065038), Encephalitis post varicella (10014603), Varicella (10046980), Varicella post vaccine (10063522).

4. Herpes Zoster

Following PT terms are included.

Herpes zoster (10019974), Herpes zoster iridocyclitis (10019980), Herpes zoster ophthalmic (10019983), Herpes zoster multi-dermatomal (10058428), Herpes zoster infection neurological (10061208), Herpes zoster oticus (10063491), Herpes zoster disseminated (10065038)

5. Varicella

Following PT terms are included.

Encephalitis post varicella (10014603), Varicella (10046980), Varicella post vaccine (10063522).

6. Infections That Require Intravenous Anti-infectious Therapy
All PTs which belong to SOC of Infections and Infestations (10021881) for which there
is an intravenous concomitant medication (antibiotics, antivirals, antifungals, etc.)
associated with that event for that patient.

10.9 **Appendix 9: Standard Toxicity Grading for Laboratory Tests According to National Cancer Institute Common Terminology** Criteria for Adverse Events (NCI-CTCAE) v4.0

Standard Toxicity Grading for Laboratory Tests According to National Cancer Institute Common Terminology Criteria for Adverse Events (NCI-CTCAE) v4.0

Common	reriii	nology	Criteria for A	uverse				U			
			Direction of		CTO	CAE Gra	ide ²		NCI		
			Change /						Ref.		
	Tes			0	1	2	3	4	Ver	Pa	Unit
	t								sion	ge	S
Test	Co	TT *4									
Name	de	Units	AE Term								
Alanine	ALT	n/a	Increase/	WNL	>ULN -	>3.0×U	>5.0×U	>20.0	4.0	107	n/a
Aminotran			Alanine		<=	LN -	LN -	×ULN			
sferase(AL			aminotransfera		3.0×UL	<=	<=				

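### The malignancy event of special interest is a closed list of 12 preferred terms, so a cancer coded to any other term drops out of the malignancy count, rate and confidence interval

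*SAP*

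**What the plan says.** SAP 10.8 (Appendix 8), item 2, builds the malignancy category from preferred terms alone. The list opens with "Diffuse large B-cell lymphoma (10012818), Bladder cancer (10005003), Breast cancer (10006187), Carcinoma in situ (10061450), Colon cancer (10009944") and goes on to gastric cancer, renal cancer, squamous cell carcinoma, small cell lung cancer stage unspecified, extraskeletal chondrosarcoma, lymphoma and thyroid cancer: 5 + 7 = 12 terms. Nothing says how the terms were chosen or what happens to a malignant term not on the list.

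Two infection items in the same appendix are open-ended. Item 1 is any "AE which belongs to SOC of Infections and infestations (10021881) and regarded as serious". Item 6 takes "All PTs which belong to SOC of Infections and Infestations (10021881) for which there" is an associated intravenous anti-infective.

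The appendix feeds two kinds of output, and both sections name it as the source of the definition:

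- SAP 7.5.1.1: "The number and percentage of subjects with TEAEs of special interest", repeated by region in SAP 7.8.2.
- SAP 7.5.1.2: "Patient-Year analysis for following specified AE will also be conducted by Definition 1 with 95% confidence interval", also by time interval and subgroup.

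Under Definition 1 the numerator is the number of subjects with at least one event. For everyone else the rule is: "If subjects had no predefined AE, then the duration of these subjects are summed as from initial dose through follow-up".

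**The concern.** Malignancy is a broad category that no short list of terms can be relied on to cover. If the SAP is followed as written, a subject whose only cancer is coded outside the 12 terms is left out of the malignancy n (%), the Definition 1 rate and its CI, and every interval, subgroup and regional version of them. That subject also contributes person-time as if event-free. The error has one direction: an omitted case can only lower the figures.

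This matters because long-term safety is a stated objective of the study (Protocol 2.1) and Protocol 1.4 asks investigators to pay particular attention to malignancies. These outputs are the only malignancy-specific subject count, and the only malignancy rate with a CI, that the SAP plans. The protocol itself treats malignancy generically: a malignant tumour is a discontinuation criterion (Protocol 3.4, item 6) and is always serious (Protocol Appendix 3). The SAP narrows that concept without explanation.

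**Working it through.** The documents give no malignancy count or rate for RAJ2, so there is no figure to reproduce. The check has three parts.

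**1. Does the list cover cancers the sponsor already knew of?** Protocol 1.4 names three malignancies reported across completed and ongoing ASP015K studies up to 5 December 2013. Matching them to the 12 terms by plain meaning:

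| Reported case | Matching listed term |
|---|---|
| Stomach cancer | Gastric cancer |
| Uterine sarcoma (the only one judged related) | none |
| Chronic myelogenous leukemia | none |

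One of three matches. These are programme-wide cases, and the documents do not say whether any arose in RAJ2. The comparison shows a gap in the definition, not a miscount.

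**2. Effect on the numerator.** If *m* of *A* subjects with cancer have only unlisted terms, the count falls by *m/A*. The values of *A* and *m* are assumptions.

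| | A = 5 | A = 10 | A = 15 |
|---|---|---|---|
| m = 0 | 0% | 0% | 0% |
| m = 1 | 20% | 10% | 6.7% |
| m = 2 | 40% | 20% | 13.3% |

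**3. Effect on the rate and CI.** SAP 7.5.1.2 gives rate = 100 × A/T and limits = 100 × exp(log(A/T) ± 1.96 × √(1/A)). Assume T = 2,400 patient-years (800 subjects × 3 years) and add 28/365.25 = 0.077 patient-years for each missed case, the time to the scheduled follow-up visit.

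| Subjects counted | Rate per 100 PY | 95% CI |
|---|---|---|
| 10 (none missed) | 0.417 | 0.224 to 0.774 |
| 9 (one missed) | 0.375 | 0.195 to 0.721 |
| 8 (two missed) | 0.333 | 0.167 to 0.666 |

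For the first row: 100 × 10/2,400 = 0.417; exp(1.96 × √(1/10)) = exp(0.620) = 1.859; 0.417/1.859 = 0.224 and 0.417 × 1.859 = 0.774.

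The person-time part is negligible if treatment stops promptly, as Protocol 3.4 item 6 implies. The follow-up window in Protocol 7.8.1 is 21 to 35 days, so a missed case adds at most 35/365.25 = 0.096 patient-years. That is 0.012% of 800 patient-years and 0.0017% of 5,600 (800 subjects × 1 and × 7 years, both assumed). The loss from the numerator is what matters.

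**The case against.** The strongest reply is that the list may record the malignant terms already coded in the study. It is oddly specific in places and omits common cancers, the study is open-label and started in 2012, and the SAP pages are dated November 2019. On that reading nothing is missed. This is plausible, but it is inference: the SAP states neither the source of the list nor a cut-off, and gives no rule for a term that appears later.

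Second, no case is hidden. Every malignant tumour is an SAE, and because "Subjects reporting more than one AE within a SOC will be counted only once for the SOC total", the neoplasm SOC row of the serious-TEAE table still counts each such subject. Cases should also appear in the tables of events leading to discontinuation and in the listings. In addition, "The number of TEAEs and TEAEs per 100 PYs will be provided by Definition 2, for all TEAEs (if analyzable) by SOC and PT". All of this stands, and it limits the seriousness of the point. It does not replace the missing output: a SOC row may include non-malignant terms, Definition 2 counts events rather than subjects, and none of these tables gives a malignancy-only subject rate with a CI.

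Third, the contrast within the appendix is less stark than it looks. Items 3 to 5 (herpes zoster and varicella) are also term lists, and items 1 and 6 apply a filter to the SOC. That is correct, but zoster and varicella are narrow entities that a list can cover. Malignancy is the only broad category closed in this way. An unfiltered neoplasm SOC would indeed be too wide, so a filter for malignant terms is needed there too.

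Finally, in the example the intervals overlap almost entirely and there is no comparator. That bears on how much one missed case would change interpretation, not on whether the count is right.

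**Conclusion.** The concern holds. As written, the rule counts a subject with an unlisted cancer as free of malignancy, and no other provision widens the list: neither the case review in Protocol 7.8 nor the clause in SAP section 1 on justifying changes in the study report adds terms. The size in RAJ2 is unknown and may be zero. Under the assumed counts of 5 to 15 affected subjects, one missed case lowers the malignancy count by 6.7% to 20%, and the rate by practically the same proportion.

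Because every case stays visible elsewhere, this should be fixed before lock but does not threaten the safety reporting as a whole. The conclusion about the wording is firm. The illustrative sizes rest on assumed values of *A*, *m* and *T*, and the match to the three programme cases rests on plain meaning rather than on their actual coding. The statement that the error can only lower the figures applies to omitted terms. Because the list includes carcinoma in situ, the net change under a new definition also depends on whether in situ disease is to count.

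**What to change.** Redefine item 2 of SAP Appendix 8 as every TEAE that is a malignant neoplasm. Identify these events by a standard MedDRA malignancy grouping, or by medical review before lock of all preferred terms in the neoplasm SOC. Reconcile the result with the malignant-tumour SAEs that Protocol Appendix 3 requires. Keep the 12 terms only as examples. State explicitly whether in situ carcinoma and non-melanoma skin cancer count, since the list now includes carcinoma in situ and squamous cell carcinoma without a rule.

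The cost is a change of SAP wording and one medical review of neoplasm terms. No new data are collected and the Definition 1 formula is unchanged.
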